Primary Objective: The primary objective of this study is to determine whether anodal (A-tDCS) applied to L IFG along with verb therapy can improve naming outcome in individuals with PPA. A randomized, double-blind, sham controlled, within-subject crossover design will be used because this allows each participant to serve as their own control. Participants will be randomly assigned to receive either a tDCS intervention period followed by a sham intervention period, or sham followed by tDCS. Participants will receive 15 training sessions within the tDCS intervention period and 15 sessions within the sham intervention period. Each participant will receive 3-5 sessions per week depending on their preference and availability. The tDCS and sham intervention periods will be separated by an 8 week "wash out period". Language will be evaluated before therapy, one week after therapy, and 8 weeks after therapy for each intervention period.

Aim 1: To evaluate the effects of A-tDCS applied to left IFG during VNeST therapy on word retrieval of trained verbs, and generalization to untrained verbs and nouns in a randomized double-blind, sham controlled, within-subject crossover trial design. The Object Action Naming Battery (OANB) (Druks, 2000) will be used to evaluate verb and noun retrieval by testing participants at baseline and at 1 and 8 weeks post-treatment. The OANB tests confrontational naming of 162 objects and 100 actions. The verbs on the OANB will be separated into trained (OANBtrained) and untrained (OANBuntrained) verbs, which will be personalized for each participant, in order to evaluate generalization. The primary outcome variable will be change in naming accuracy of OANBtrained verbs. Secondary outcome variables will be change in naming accuracy of OANBuntrained verbs and untrained nouns (OANBnouns), as well as

Hypothesis 1A. Anodal tDCS (A-tDCS) plus VNeST therapy (A-tDCS+therapy) will significantly improve word retrieval of trained transitive verbs (from baseline to 1 week and 8 weeks post treatment).

Hypothesis 1B. A-tDCS+therapy will generalize to other untreated verbs and nouns from baseline to 1 week and 8 weeks post treatment.

Hypothesis 1C. Combined A-tDCS+therapy will result in greater improvement in functional communication skills compared to sham+therapy.

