Secondary Objective: The secondary objective of this study is to examine which patterns of atrophy predict the best response to treatment. This will help improve the selection of specific treatments for individual patients in the future.

Aim 2: To investigate which patterns of atrophy are associated with greatest response to treatment (improvement in naming verbs) in individuals with PPA following A-tDCS+therapy vs. sham+therapy.

Hypothesis: People with more IFG damage tend to have more trouble with verbs, so we predict they are likely to show the most change in verb naming following A-tDCS+therapy. It is possible that this hypothesis is incorrect, and they will show the least benefit from A-tDCS due to atrophy in IFG. It may be that people with more atrophy in other areas are going to benefit the most from this intervention.

3. Background (briefly describe pre-clinical and clinical data, current experience with procedures, drug or device, and any other relevant information to justify the research)

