Visit 3-4: These sessions involve detailed language testing (see below) including computerized naming assessments. This battery will be the baseline language testing. A screening task will be administered prior to the baseline language testing. Participants must achieve at least 65% accuracy on screening task (comparable to treatment task) on 1 of 3 attempts. The screening test is administered to ensure that the participant understands the treatment task requirement. The probability that a patient will achieve $>65\%$ accuracy by chance on each of the three tries is low: $p<0.05$. If a participant is unable to reach this level of accuracy, study enrollment will be discontinued. A naming test will also be administered as part of baseline testing examining the ability to name nouns and verbs from pictures. Participants who's correct naming score exceeds an average of 80% accuracy will be excluded to leave at least a 20% improvement margin. That is, participants who already score close to ceiling may have limited room for naming improvement.

Visit 5-19: These sessions will involve the treatment sessions for the first intervention period. Prior to the start of treatment, participants will be randomly assigned to receive either "tDCS then sham" or "sham then tDCS". For example, if a participant is randomly assigned to received "tDCS then sham", the first intervention period of 15 sessions will be tDCS+ language treatment and the second intervention period will be 15 sessions of sham + language treatment.

Date: 01/11/2019
Principal Investigator: [name]
Application Number: IRB00174879

Visit 20: This visit will involve 1 week post treatment language testing. This visit will be similar to Visits 3-4.

Visit 21: 8-week follow up visit. Testing during this session will be considered as baseline testing for phase 2 intervention.

Visit 22-36: These sessions will involve the treatment sessions for the second intervention period. The opposite tDCS condition will be implemented here. For example, if a participant is randomly assigned to received “tDCS then sham”, the second intervention period will be 15 sessions of sham + language treatment.

Visit 37: 1-week follow up language testing after second intervention period.

Visit 38: 8-week follow up language testing after second intervention period.

Procedures for Screening (Visit 1)

The following procedures will be performed:

1. Administer the tDCS safety screening and MRI safety screening

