For Aim 1, Hypothesis 1a This hypothesis states that Anodal tDCS (A-tDCS) plus VNeST therapy (A-tDCS+therapy) will significantly improve word retrieval of trained transitive verbs (from baseline to 1 week and 8 weeks post treatment). In the proposed study each participant will either receive tDCS (T) in the first intervention period followed by sham (S) in the second period (order = TS), or they will receive sham in the first period followed by tDCS (order = ST). For each participant, i , we will measure the change in word retrieval on the OANBtrained due to real tDCS stimulation by subtracting word retrieval performance accuracy on the OANBtrained before tDCS stimulation from the testing period 1 week following tDCS stimulation ($\delta Y_{i,tDCS}$). The identical measure will be computed for sham stimulation ($\delta Y_{i,sham}$). The data will be analyzed ($order_i, \delta Y_{i,tDCS}, \delta Y_{i,sham}$) for participants $i = 1, \dots, n$. Three models will be evaluated: the model of tDCS vs. sham, the model that adds the period effect, and the model that adds the interaction (a carryover effect). The predictive accuracy of these 3 models will be compared using the leave-one-out cross-validation R^2 . The model that best fits the data (the model with the highest R^2) will then be used to estimate the effect of tDCS relative to sham. This procedure will be repeated to determine changes from baseline to a period 8 weeks after treatment conclusion.

Sample Size Determination

We expect to enroll at least 50 participants with PPA over five years, and expect 45-50 will complete the study. This sample size is based on data collected from a separate study, IRB protocol number NA_00078932, PI [name]. *The effect size for anodal tDCS stimulation was 0.6 for trained items and 1.5 for untrained items.* We determined the number of participants to study, in order for the analysis to have 80% power to detect an effect size as low as 0.6. Allowing for 10% attrition, a sample size of 50 was chosen.

Missing Data

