We plan to minimize missing data by avoiding prolonged intervals between stimulations: 2 months may seem long with regard to the literature, but it is a reasonable length of time to be able to determine sustainability of any therapy. To minimize possible biases, analyses will be by intention to treat; any missing data will be addressed with the technique of multiple imputation (Rubin, 2004), generally recognized as best for handling missing data (Little et al., 2012).

Secondary Analyses

For Aim 1, Hypothesis 1b This hypothesis states that A-tDCS+therapy will generalize to other untreated verbs and nouns from baseline to 1 week and 8 weeks post treatment. The analyses will be identical to those described for Aim 1, Hypothesis 1a, except data from untreated verbs (OANBuntrained) and OANBnouns (untrained) will be used.

Aim 1, Hypothesis 1c Hypothesis 1c states that combined A-tDCS+therapy will result in greater improvement in functional communication skills compared to sham+therapy. Changes to functional communication skills resulting from A-tDCS+therapy vs. sham will be assessed using the ASHA FACS scale.

For Aim 2, Hypothesis 1: The proposed study aims to determine which patterns of baseline atrophy will predict the best response to A-tDCS plus a verb treatment using sentence building in individuals with PPA. People with more IFG damage tend to have more trouble with verbs, so we predict they are likely to show the most change in the primary outcome variable (OANBtrained verbs) with A-tDCS+therapy. It is possible that this hypothesis is incorrect, and they will show the least benefit from tDCS due to atrophy in IFG. It may be that people with more atrophy in other areas are going to benefit the most. Confirmation of either hypothesis will help select the best candidates for treatment. The area of peak atrophy (greatest difference between volume of each of the parcels on the JHU-MNI atlas in the participant compared to controls) will be identified for each participant. We will group participants by area of peak atrophy, and compare groups for each outcome variable, using Kruskal-Wallis one-way analysis of variance, for each outcome variable. As an exploratory analysis, we will also evaluate Spearman's correlations between the primary outcome variable and baseline volume in 5 regions of interest (areas affected in PPA: left IFG, left inferior temporal gyrus, left temporal pole, left superior temporal gyrus, and left supramarginal gyrus).

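### The Aim 2 atrophy tests ignore randomised order, so any difference between first-course and second-course response stays in the outcome as noise and costs some power

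*Combined protocol and SAP*

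**What the plan says.** Section 7c, Secondary Analyses, sets the Aim 2 tests. The main one is: "We will group participants by area of peak atrophy, and compare groups for each outcome variable, using Kruskal-Wallis one-way analysis of variance". An exploratory analysis examines "correlations between the primary outcome variable and baseline volume in 5 regions of interest". Neither includes order or period as a factor, stratum or covariate.

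The response is not given as a formula. Section 7c predicts that people with more IFG damage are those of whom it can be said that "they are likely to show the most change in the primary outcome variable (OANBtrained verbs) with A-tDCS+therapy", which points to the change in the tDCS period alone. Section 2 (Aim 2) speaks of response "in individuals with PPA following A-tDCS+therapy vs. sham+therapy", which can be read as tDCS minus sham.

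On the design, section 2 says: "Participants will be randomly assigned to receive either a tDCS intervention period followed by a sham intervention period, or sham followed by tDCS". It adds: "Participants will receive 15 training sessions within the tDCS intervention period and 15 sessions within the sham intervention period". In section 4a the visit 8 weeks after period 1 supplies the period 2 starting value: "Testing during this session will be considered as baseline testing for phase 2 intervention".

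For Aim 1, section 7c carries order in the data and compares three models: treatment only, treatment plus period, and treatment plus period plus interaction. Hypothesis 1b is given the same analysis. Aim 2 is not.

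**The concern.** In one order the tDCS change is a first-course response. In the other, where "they will receive sham in the first period followed by tDCS (order = ST"), it is a second-course response from a later baseline, after a full course of the same language therapy. If first-course and second-course change scores differ on average, the one-way rank test and the plain correlations treat that difference as unexplained variation between people. Correlations with regional volume shrink, differences between atrophy groups are harder to detect, and a real predictor is more likely to be missed. The plan wants Aim 2 to help choose candidates for treatment, and order is known for every participant, so leaving it out gives up precision that costs almost nothing to keep.

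**Working it through.** **The plan's own figure.** No power, alpha or number of groups is stated for Aim 2. The only sample-size figure is N = 50 for Aim 1 (effect size 0.6, 80% power, 10% attrition). It can be matched as a two-sample per-group size at two-sided 0.05: 2 × (1.960 + 0.842)² / 0.6² = 43.6, so 44 (45 with the t distribution). Dividing by 0.9 gives 49 (50 with t). The plan expects 45–50 completers; 45 is used below.

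**Assumptions not in the documents.** Two-sided alpha 0.05; orders split about 1:1 (22/23); normal errors; true correlation 0.40 between regional volume and response; three equal atrophy groups for Kruskal-Wallis; period effect P, in SDs of a change score, from 0 to 1.

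**Variance, response = tDCS change.** The period effect adds P to about half the participants, which contributes variance P²/4. Relative variance is 1 + P²/4:
- P = 0.25: 1.02, so 45 people carry the information of 45/1.016 = 44
- P = 0.5: 1.06, so 45/1.0625 = 42
- P = 1: 1.25, so 45/1.25 = 36

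**Variance, response = tDCS minus sham.** The period effect enters as +P in one order and −P in the other, which contributes P². The difference has variance 2(1 − ρ), where ρ is the within-person correlation of the two changes. Relative variance is 1 + P²/[2(1 − ρ)]. At P = 1 it is 1.5 for ρ = 0 and 2 for ρ = 0.5. At P = 0.5 it is 1.125 and 1.25.

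**Hand check of Spearman power.** Divide 0.40 by the square root of the relative variance to get r, convert by r_s = (6/π)·arcsin(r/2), and compare atanh(r_s)/√(1.06/42) with 1.96.
- No period effect: r_s = 0.385, z = 2.55, power 72%
- tDCS change, P = 1: r = 0.358, r_s = 0.343, z = 2.25, power 62%
- tDCS minus sham, P = 1: power 53% (ρ = 0) and 42% (ρ = 0.5)

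**Simulated power, unadjusted v order-adjusted** (Spearman, true correlation 0.40):

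| Response | P = 0 | P = 0.25 | P = 0.5 | P = 1 |
|---|---|---|---|---|
| tDCS change | 74% v 73% | 73% v 73% | 71% v 73% | 62% v 73% |
| tDCS minus sham, ρ = 0 | 74% v 73% | – | 68% v 73% | 53% v 73% |
| tDCS minus sham, ρ = 0.5 | 74% v 73% | – | 62% v 73% | 41% v 73% |

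Kruskal-Wallis on the tDCS change with three equal groups behaves alike: 75% v 74% at P = 0 and 64% v 74% at P = 1, the adjusted test using responses centred within order. With the group effect set larger, for 80% power at P = 0, the figures are 77% v 78% at P = 0.5 and 69% v 78% at P = 1. Five equal groups give nearly the same.

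**Type I error.** With no true group difference, the unadjusted Kruskal-Wallis test rejects in 4–5% of simulated trials at every P tried, up to 1.5 SD.

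**The case against.** The best counter-argument is that no sizeable period effect has been shown. It is tempting to infer one from the 11–13 weeks of progressive disease (3–5 weeks of treatment plus 8 weeks) that separate the two starting points. The documents do not support that step. The response is a change score and period 2 has its own baseline, so decline in level is subtracted out, and a steady rate of decline produces no period effect. Only a changed rate of decline or a changed response to training does, and the plan gives no figure for either. It also does not say whether the same personalised verbs are trained in both courses, so even the direction is unknown. This part of the objection stands: the loss is conditional, and at 0.25 SD it is negligible.

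A second tempting inference is that order confounds the atrophy comparison, or that a chance imbalance of order in a small atrophy group makes false findings more likely. Randomisation rules out the first on average. On the second, an imbalance can shift a single result, but the p-value already allows for it, as the 4–5% rejection rate shows.

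A third is to take 41–53% as the power of Aim 2. Those figures need both a 1 SD period effect and the tDCS-minus-sham response, whereas section 7c points to the tDCS change. What survives is that the tests make no use of a known design factor that Aim 1 does consider, and that the response is not defined.

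**Conclusion.** The point holds as a matter of efficiency. The Aim 2 tests take no account of randomised order, so any difference in mean change between first and second course remains as noise. On the tDCS change the loss relative to an adjusted test is nil up to about 0.25 SD, about 2 points at 0.5 SD and about 11 points at 1 SD. On tDCS minus sham it is 5–11 points at 0.5 SD and 20–32 points at 1 SD. These figures rest on 45 completers, a true correlation of 0.40, alpha 0.05 two-sided, roughly equal orders and an assumed period effect. The number with a usable scan may be lower, since study MRI depends on funding.

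A reader might infer that the trial's main result or its size is in doubt. Neither is: Aim 2 is secondary with no stated power, and the primary analysis and N = 50 are untouched. Severity is low.

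**What to change.** 1. State which response Aim 2 uses: the change in the tDCS period, or tDCS change minus sham change. Sections 2 and 7c should agree.
2. Run the Kruskal-Wallis test on responses centred within randomised order. An order-stratified rank test (van Elteren type) is suitable only if the order-by-group cells are large enough. Groups defined by peak atlas parcel could leave cells very small or empty. In simulation with no period effect the stratified test lost 2 points with three equal groups (71% to 69%) and 3 points with eight unequal groups (43% to 40%).
3. Replace the plain Spearman correlations with partial Spearman correlations given order.

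Do not add baseline verb accuracy as a further covariate under this point. The plan's hypothesis is that IFG damage goes with verb difficulty and hence with more change, so conditioning on baseline accuracy could remove the association Aim 2 is asking about.

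The cost is a few lines of SAP text and about 1 point of power if there is no period effect. No new data, visits or participants are needed.

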5. Administer the Apraxia of Speech Rating Scale (Strand et al., 2014), to rate frequency and severity of particular characteristics of apraxia of speech (AOS): The Apraxia of Speech Rating Scale is a rating scale, in which speech characteristics are evaluated in terms of frequency and severity. Higher scores indicate more severe apraxia of speech. SLPs will refer to the manual for explicit instructions regarding administration and scoring procedures. Administration time will range between 10-15 minutes.

6. Administer the Pyramids and Palm Trees Test (PPTT) (Short form): The PPTT is a test of semantic processing. This test assesses the degree to which a participant can access meaning from pictures. Information from the test will help determine whether a participant's difficulty in naming or pointing to a named picture is due to a difficulty in retrieving semantic information from pictures (Breining et al., 2015; Howard & Patterson, 1992). Experimenters will refer to the manual for explicit instructions regarding administration and scoring procedures. Administration time will range between 10-20 minutes.

7. Administer the ASHA Functional Assessment of Communication Skills for Adults (FACS). This is a tool used for measuring and recording the functional communication of adults with speech, language, and cognitive communication disorders. This assessment is comprised of 43 items and assesses functional communication in four areas: social communication; communication of basic needs; reading, writing, and number concepts; and daily planning.

8. Administer naming screen used to verify that participants comprehend task requirements: Refer to computer setup for the treatment for this practice screen.

9. Administer the Object & Action Naming Battery (OANB) (see section below on Naming Assessments): The OANB consists of line drawings of 162 objects and 100 actions together with ratings for age-of-acquisition, familiarity and imageability of the verbal labels of the pictures (Druks, 2000). Experimenters will refer to the manual for explicit instructions regarding administration and scoring

procedures. Administration time will range between 30-60 minutes. Participants whose correct naming score exceeds an average of 80% on the OANB during baseline sessions will be excluded, in order to leave at least a 20% improvement margin. That is, patients who already score close to ceiling may have limited room for naming improvement as measured by the OANB.

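### Aim 2 relates raw change on a bounded naming score to atrophy without baseline naming or a stated tDCS-versus-sham contrast, so scale room could pass for an atrophy effect if gain scales with room

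*Combined protocol and SAP*

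**What the plan says.** Section 2, Aim 1, sets the outcome: "The primary outcome variable will be change in naming accuracy of OANBtrained verbs". Section 7c, Statistical Analyses, forms it by "subtracting word retrieval performance accuracy on the OANBtrained before tDCS stimulation from the testing period 1 week following tDCS stimulation", with the same calculation for sham. The score is bounded, because it is accuracy on a fixed picture set: "The OANB tests confrontational naming of 162 objects and 100 actions". Trained verbs are a personalised subset of the actions, and no selection rule is given.

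Section 7c, Secondary Analyses, gives the Aim 2 tests. The main one is: "We will group participants by area of peak atrophy, and compare groups for each outcome variable, using Kruskal-Wallis one-way analysis of variance". The exploratory one is Spearman's "correlations between the primary outcome variable and baseline volume in 5 regions of interest". Baseline naming enters neither. The reasoning for the hypothesis is: "People with more IFG damage tend to have more trouble with verbs, so we predict they are likely to show the most change".

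The Aim 2 objective in section 2 asks about response "in individuals with PPA following A-tDCS+therapy vs. sham+therapy". The section 7c text predicts change under active stimulation and does not name the quantity to be tested.

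Section 4a, item 9 (OANB), recognises that "patients who already score close to ceiling may have limited room for naming improvement as measured by the OANB", but uses this only for an eligibility cap.

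**The concern.** The hypothesis that IFG damage predicts more change is drawn from the expectation that these patients start lower. A patient who starts lower can gain more points. A positive result could therefore mean that atrophy marks responders to stimulation, or only that low scorers had more room. Raw change analysed without baseline naming does not separate the two.

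The plan intends Aim 2 to help choose candidates for treatment. The risk is that regional volume is credited with information already held in the baseline OANB, or that a response to the language therapy itself is reported as a response to tDCS.

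**Working it through.** **Plan's own figure.** The documents give no sample size, power or error rate for Aim 2. The stated 50 is for Aim 1. Assuming two-sided 5% and uncorrelated changes in the two periods, 2 × ((1.96 + 0.84)/0.6)² = 43.6, so 44; 44/0.9 = 48.9, so 49, close to 50. This does not bear on the present point. The plan expects 45-50 completers; 45 is used below.

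**Room on the scale.** Section 5 excludes picture naming below 10% and above 85%; section 4a caps it at 80%. (The two upper limits conflict and must be reconciled.) Possible gain runs from 100 − 10 = 90 points down to 100 − 80 = 20, or 100 − 85 = 15. These limits concern overall picture naming, not the trained list.

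**Mechanism, if gain is a fixed fraction g of missed items.** Gain = g × (1 − baseline). Take g = 0.5 under tDCS and 0.3 under sham:
- Baseline 20%: tDCS 40 points, sham 24, difference 16.
- Baseline 80%: tDCS 10 points, sham 6, difference 4.

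The spread due to baseline alone is 30 points for tDCS change and 12 for the difference. With equal g it is zero for the difference.

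**Simulation assumptions (none from the documents).** n = 45; two-sided 5% test; volume related to baseline naming with correlation 0.3, 0.5 or 0.7 and to nothing else; no carryover.
- Setting A: 30 trained verbs, binomial scores, true baseline 0.10 + 0.75 × Φ(latent), the correlation being on the latent scale.
- Setting B: baseline mean 45%, SD 20, truncated to 10-80%; noise SD 10 points.

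Each cell had 1,500 to 3,000 trials. Percent of trials significant at correlation 0.3 / 0.5 / 0.7:

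| Gain rule | Spearman, tDCS change | Spearman, tDCS minus sham |
|---|---|---|
| A: 50% of missed verbs (sham 30%) | 24 / 60 / 90 | 7 / 12 / 19 |
| A: 30% (sham 15%) | 14 / 33 / 63 | 7 / 9 / 13 |
| B: 40% of room (sham 25%) | 14 / 32 / 65 | 6 / 9 / 9 |
| B: 30% in both, tDCS no better than sham | 11 / 24 / 44 | 4-6 |
| A: constant 15 points | 5 / 5 / 5 | not tabulated |
| A: logit shift 0.8 | 6 / 7 / 9 | not tabulated |
| B: constant 20 points (sham 10) | 5 / 5 / 5 | 5-6 |
| B: constant 35 points (sham 20) | 7 / 10 / 15 | 5 / 6 / 10 |

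In the 35-point row the ceiling itself acts. If every trained verb is failed at baseline, the rate is about 5%.

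**Kruskal-Wallis.** With three equal groups cut by volume, a simplification of peak-atrophy groups, rejection on tDCS change in setting A is 14 / 40 / 77% (50% gain) and 10 / 21 / 43% (30% gain).

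**Effect of adjusting for observed baseline.**
- tDCS change, proportional gain, setting A: 5 / 8 / 12% (50%) and 7 / 9 / 16% (30%).
- tDCS change, constant 15 points: 8 / 13 / 27%, worse than the unadjusted 5%. Logit shift: 7 / 11 / 21%. Baseline error is subtracted in the outcome and also sits in the covariate, and volume then stands in for true baseline.
- tDCS-minus-sham change, adjusted for the average of the two period baselines: 4-7% under proportional, constant and logit rules. The two baseline errors enter the difference with opposite signs, so they are uncorrelated with the average.

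**The case against.** The strongest reply is that the large figures come from one assumed mechanism. Nothing in the documents says that patients regain a fixed share of missed verbs. With a modest constant gain or a logit shift there is almost nothing to correct, and if more impaired patients learn less the bias could reverse. This stands, so the range has to be shown with those cases included.

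Second, the Aim 2 objective already names the contrast with sham, which removes most of the inflation. This also stands, except that section 7c does not say the difference is what is tested.

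Third, personalised lists might equalise baseline. They might, but no rule is given. Kruskal-Wallis is also planned for every outcome variable, including untrained verbs and nouns, where training lists of failed verbs would not necessarily help.

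Fourth, the Spearman analysis is exploratory, and prediction through severity is a fair question when selecting patients. Both are true and limit the weight of the point. The Kruskal-Wallis comparison is not labelled exploratory and has the same gap.

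A reader might go further and infer that Aim 2 will produce a false atrophy finding, or that only a baseline-adjusted association can count. The documents support neither: they do not fix how gain depends on starting score, and adjusting a single-period change for an error-prone baseline can itself create an association.

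**Conclusion.** The gap is real but conditional. The plan tests raw change on a bounded score, has no baseline naming term, and leaves the tDCS-versus-sham contrast out of the Aim 2 analysis. If gain scales with room, Spearman gives a spurious association in about 14-90% of trials on tDCS change where tDCS outperforms sham, and about 6-20% on the difference, over volume-baseline correlations of 0.3-0.7. With modest constant gain or a constant logit shift the rate is about 4-9%, and for trained verbs the artefact vanishes if all were failed at baseline. Which case applies cannot be read from the documents. This is a cheap improvement to consider; it does not touch the primary analysis.

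**What to change.** In section 7c, Aim 2:
1. Define response as each participant's tDCS change minus sham change, in line with the Aim 2 objective.
2. Report Kruskal-Wallis and Spearman unadjusted and, beside them, adjusted for pre-treatment naming on the same item set, using the average of the two period baselines (rank ANCOVA and partial Spearman).
3. Do not describe a region as predicting tDCS response beyond initial severity when the two results disagree. Do not make survival after adjustment the sole test of whether a region is predictive.
4. State how trained verbs are chosen, since this decides whether the issue arises for that outcome.

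Cost: SAP wording only; the OANB is already given before each period. The difference is noisier than tDCS change alone, and adjustment uses one degree of freedom. An effect acting wholly through severity will show only in the unadjusted result. If tDCS change alone is also reported, its adjusted version needs the caution above. The second-period baseline may retain some first-period gain, which the simulations assume away.
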